10.3.1. Adverse Event

AE Definition

An AE is defined as any untoward medical occurrence in clinical study participants administered a pharmaceutical (investigational or non-investigation) product. An AE does not necessarily have a causal relationship with the study intervention. An AE can therefore be any unfavourable and unintended sign (including an abnormal laboratory finding), symptom, or disease temporally associated with the use of a medicinal (investigational or non-investigational) product (definition as per ICH).
 
This will also cover any AEs occurring after study intervention(s) including administration with the challenge agent in viral challenge studies.

Unsolicited AEs

Unsolicited AEs are defined as any AEs observed by the participant or PI/investigator which are not pre-listed on the symptom diary card. Unsolicited AEs will be collected upon signature of study-specific ICF until the end of the study. Any unsolicited AEs observed by the PI/investigator and/or reported by the participant must be recorded in the eCRF regardless of causality in relationship with IMP.

Events Meeting the AE Definition

 Exacerbation of a pre-existing illness. Increase in frequency or severity of a pre-existing episodic condition. A condition detected or diagnosed after study intervention administration even though it may have been present prior to the start of the study. A complication that occurs during a hospitalisation. A clinically significant change in laboratory parameter.

Events NOT Meeting the AE Definition

 Medical or surgical procedures (e.g., surgery, endoscopy, tooth extraction, transfusion); the condition that leads to the procedure is an AE. Pre-existing disease or condition present or detected prior to start of study intervention administration that does not worsen (including screening findings such as abnormal laboratory results).

- Hospitalisation for elective surgery, social and/or convenience admissions provided they are arranged before the start of study intervention administration and the reason does not worsen.
- Over-administration of either the study intervention or concomitant medication without any signs or symptoms.
- An uncomplicated pregnancy or an induced elective abortion to terminate a pregnancy without medical reason.
- Typical/normal/solicited viral infection symptoms on symptom diary cards.

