10.9.1. Adverse Events

All adverse events (AE) will be coded using MedDRA, Version 25.0.

An adverse event is defined as treatment emergent if the onset date is on or after the date of first dosing with IMP. Should any onset date for an adverse event be missing or only a partial date recorded (such that it cannot be determined if the event onset was prior to start of IMP or not) then it will be assumed that the event is treatment emergent, unless the adverse event stop date indicates otherwise.

Similarly, an AE is defined as challenge emergent if the onset date is on or after the date of inoculation. Should any onset date for an adverse event be missing or only a partial date recorded (such that it cannot be determined if the event onset was prior to inoculation or not) then it will be assumed that the event is challenge emergent, unless the adverse event stop date indicates otherwise.

An AE can be both challenge emergent and treatment emergent. Any AE with an onset date earlier than the inoculation date will be classified as a pre-treatment AE.

If a participant experiences more than one adverse event with the same preferred term, that preferred term will be counted only once. It will be assigned the greatest observed severity and the strongest relationship to IMP among those events for the tables in which those characteristics are summarised.

Pre-treatment AEs will be identified in a patient listing.

A summary of treatment-emergent AEs will be presented by treatment group showing the number of events, number of participants with events (also split by severity; mild, moderate, severe), number of participants with SAEs, number of participants with related events, number of participants with events

leading to early withdrawal from the study and the number of participants with events leading to early discontinuation of IMP.

Further summaries will present the treatment-emergent AEs by:

- Treatment group, SOC and PT.
- Treatment group, SOC, PT and severity.
- Treatment group, SOC, PT and relationship to IMP.

Further summaries will present the challenge-emergent AEs by:

- Treatment group, SOC, PT and relationship to challenge agent.

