Min, Max	XX, XX	XX, XX		XX, XX	XX, XX
[Repeat for all days during Quarantine Period]					

Note: Days are relative to first administration of IMP.

Note: Total symptom scores on the day of the first administration of IMP can be prior to or after dosing, depending on whether dosed in the morning or evening.

Table 14.2.3.7.1
 Time to Symptom Resolution by 10-Item Diary Card from Initial Administration of IMP to 24-Hours Symptom Free
 ITT-I Population

Time (days)	Treatment Group	
	RV299 (N=xx)	Placebo (N=xx)
n	XX	XX
Mean (SD)	XX.X (XX.XX)	XX.X (XX.XX)
GM (GSD)	XX.X (XX.XX)	XX.X (XX.XX)
%CV	XX.XX	XX.XX
Median	XX.X	XX.X
Q1, Q3	XX.X, X.XX	XX.X, X.XX
Min, Max	XX, XX	XX, XX

Note: Time to Symptom Resolution from Initial Administration of IMP = (Date and time of symptom resolution - Date of and time of assessment at time of IMP administration) + 1.

This layout will be utilised for the following tables:

Table 14.2.3.8.1 Time to Symptom Resolution by 10-Item Diary Card from Peak Total Symptom Score to 24-Hours Symptom Free - ITT-I Population
 Table 14.2.3.9.1 Time to Peak Symptom Score by 10-Item Diary Card from Initial Administration of IMP - ITT-I Population

The layout will be repeated for the following tables, without the GM (GSD) row:

Table 14.2.4.1.1 Total Weight of Mucus Produced from Initial Administration of IMP to Quarantine Discharge - ITT-I Population
 Table 14.2.4.2.1 Total Number of Tissues Used from Initial Administration of IMP to Quarantine Discharge by Assessment - ITT-I Population

CCI

Table 14.3.1.67
 Overall Summary of Treatment Emergent Adverse Events
 Safety Population

	Treatment Group					
	RV299 (N=xx)		Placebo (N=xxx)		Overall (N=xx) (%)	
	n	(%)	n	(%)	n	(%)
Number of Events	XX		XX		XX	
Number of Participants with any Adverse Event	XX	(XX.X)	XX	(XX.X)	XX	(XX.X)
Mild	XX	(XX.X)	XX	(XX.X)	XX	(XX.X)
Moderate	XX	(XX.X)	XX	(XX.X)	XX	(XX.X)
Severe	XX	(XX.X)	XX	(XX.X)	XX	(XX.X)
Number of Participants with any Serious Adverse Event	XX	(XX.X)	XX	(XX.X)	XX	(XX.X)
Number of Participants with any Related Adverse Event	XX	(XX.X)	XX	(XX.X)	XX	(XX.X)
Number of Participants with any Adverse Event Leading to Withdrawal from the Study	XX	(XX.X)	XX	(XX.X)	XX	(XX.X)
Number of Participants with any Adverse Event Leading to Discontinuation of IMP	XX	(XX.X)	XX	(XX.X)	XX	(XX.X)

Note: Treatment emergent events are those events with an onset on or after the start of IMP dosing.

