Note: If a participant experiences more than one event, then the event with the worst severity or strongest relationship is included in the relevant level of summarisation.

Note: Related = 'Unlikely', 'Possibly', 'Probably', 'Definitely' or 'Not assessed'.

Note: Adverse Event Leading to Discontinuation from the Study = Participant withdrew from the study due to an adverse event.

Note: Adverse Event Leading to Discontinuation of Dosing = Action taken of 'Trial/Study drug permanently discontinued'.

Note: Percentages are based on the safety population.

Table 14.3.1.68
 Treatment Emergent Adverse Events by System Organ Class and Preferred Term
 Safety Population

System Organ Class/ Preferred Term [1]	Treatment Group			
	RV299 (N=xx)	n (%)	Placebo (N=xxx)	n (%)
Number of Events	XX		XX	
Number of Subjects with any adverse event	XX	(XX.X)	XX	(XX.X)
System Organ Class 1	XX	(XX.X)	XX	(XX.X)
Preferred Term 1	XX	(XX.X)	XX	(XX.X)
Preferred Term 2	XX	(XX.X)	XX	(XX.X)
System Organ Class 2	XX	(XX.X)	XX	(XX.X)
Preferred Term 1	XX	(XX.X)	XX	(XX.X)
Preferred Term 2	XX	(XX.X)	XX	(XX.X)

[1] MedDRA Version 25.0.

Note: Treatment emergent events are those events with an onset on or after the first administration of IMP.

Note: Table shows distinct number of participants with events for each system organ class/preferred term.

Note: Percentages are based on the safety population.

Table 14.3.1.3
Treatment Emergent Adverse Events by System Organ Class, Preferred Term and Severity
Safety Population

System Organ Class/ Preferred Term [1]	Treatment Group			
	RV299 (N=xx)	n (%)	Placebo (N=xxx)	n (%)
System Organ Class 1				
Mild	XX	(XX.X)	XX	(XX.X)
Moderate	XX	(XX.X)	XX	(XX.X)
Severe	XX	(XX.X)	XX	(XX.X)
Preferred Term 1				
Mild	XX	(XX.X)	XX	(XX.X)
Moderate	XX	(XX.X)	XX	(XX.X)
Severe	XX	(XX.X)	XX	(XX.X)
Preferred Term 2				
Mild	XX	(XX.X)	XX	(XX.X)
Moderate	XX	(XX.X)	XX	(XX.X)
Severe	XX	(XX.X)	XX	(XX.X)
System Organ Class 2				
Mild	XX	(XX.X)	XX	(XX.X)
Moderate	XX	(XX.X)	XX	(XX.X)
Severe	XX	(XX.X)	XX	(XX.X)
Preferred Term 1				
Mild	XX	(XX.X)	XX	(XX.X)
Moderate	XX	(XX.X)	XX	(XX.X)
Severe	XX	(XX.X)	XX	(XX.X)

[1] MedDRA Version 25.0.

Note: Treatment emergent events are those events with an onset on or after the first administration of IMP.

Note: This table shows distinct number of participants with events for each system organ class/preferred term/severity. If a participant experienced a specific event more than once then the event with the worst severity is summarised.

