Note: Percentages are based on the safety population.

Table 14.3.1.4
Treatment Emergent Adverse Events Related to RV299 by System Organ Class and Preferred Term
Safety Population

System Organ Class/ Preferred Term [1]/ Relationship	Treatment Group			
	RV299 (N=xx)	n (%)	Placebo (N=xxx)	n (%)
System Organ Class 1	XX	(XX.X)	XX	(XX.X)
Not Assessed	XX	(XX.X)	XX	(XX.X)
Unlikely Related	XX	(XX.X)	XX	(XX.X)
Possibly Related	XX	(XX.X)	XX	(XX.X)
Probably Related	XX	(XX.X)	XX	(XX.X)
Definitely Related	XX	(XX.X)	XX	(XX.X)
Preferred Term 1	XX	(XX.X)	XX	(XX.X)
Not Assessed	XX	(XX.X)	XX	(XX.X)
Unlikely Related	XX	(XX.X)	XX	(XX.X)
Possibly Related	XX	(XX.X)	XX	(XX.X)
Probably Related	XX	(XX.X)	XX	(XX.X)
Definitely Related	XX	(XX.X)	XX	(XX.X)
Preferred Term 2	XX	(XX.X)	XX	(XX.X)
Not Assessed	XX	(XX.X)	XX	(XX.X)
Unlikely Related	XX	(XX.X)	XX	(XX.X)
Possibly Related	XX	(XX.X)	XX	(XX.X)
Probably Related	XX	(XX.X)	XX	(XX.X)
Definitely Related	XX	(XX.X)	XX	(XX.X)
System Organ Class 2	XX	(XX.X)	XX	(XX.X)
Not Assessed	XX	(XX.X)	XX	(XX.X)
Unlikely Related	XX	(XX.X)	XX	(XX.X)
Possibly Related	XX	(XX.X)	XX	(XX.X)
Probably Related	XX	(XX.X)	XX	(XX.X)
Definitely Related	XX	(XX.X)	XX	(XX.X)
Preferred Term 1	XX	(XX.X)	XX	(XX.X)
Not Assessed	XX	(XX.X)	XX	(XX.X)
Unlikely Related	XX	(XX.X)	XX	(XX.X)
Possibly Related	XX	(XX.X)	XX	(XX.X)
Probably Related	XX	(XX.X)	XX	(XX.X)
Definitely Related	XX	(XX.X)	XX	(XX.X)

[1] MedDRA Version 25.0.

Note: Treatment emergent events are those events with an onset on or after the first administration of IMP.

Note: This table shows distinct number of participants with events for each system organ class/preferred term/relationship. If a participant experiences a specific event more than once then the event with the greatest relationship is summarised.

Note: Only the subset of AEs that are judged to be related to IMP have been considered (i.e. relationship = Possibly Related/Probably Related/Definitely Related/Not Assessed) in the table.

Note: Percentages are based on the safety population.

This layout will be utilised for the following table:

Table 14.3.1.5 Adverse Events Related to Challenge Agent by System Organ Class and Preferred Term - Safety Population

With the following footnote:

Note: Only the subset of AEs that are judged to be related to challenge agent have been considered (i.e. relationship = Possibly Related/Probably Related/Definitely Related/Not Assessed) in the table.

Table 14.3.2
Haematology Parameters: Summary
Safety Population

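### Treatment-emergent is defined by onset date alone, so an AE that starts between challenge and the first-dose date and worsens on IMP is missing from the four IMP adverse event tables unless the site re-records it

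*SAP*

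**What the plan says.** SAP 10.9.1 sets three classes by onset date.

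- Treatment-emergent: "An adverse event is defined as treatment emergent if the onset date is on or after the date of first dosing with IMP".
- Challenge-emergent: "Similarly, an AE is defined as challenge emergent if the onset date is on or after the date of inoculation".
- Pre-treatment: "Any AE with an onset date earlier than the inoculation date will be classified as a pre-treatment AE".

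The shells in SAP 14 repeat the onset rule. The overall summary carries "Note: Treatment emergent events are those events with an onset on or after the start of IMP dosing", and the SOC/PT, severity and related-to-RV299 tables carry "Note: Treatment emergent events are those events with an onset on or after the first administration of IMP". None of these adds a clause on worsening.

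For the IMP, SAP 10.9.1 states "A summary of treatment-emergent AEs will be presented by treatment group", and the further tables by SOC and PT, by severity and by relationship to IMP are also limited to treatment-emergent events. In the list in SAP 13.2 these are Tables 14.3.1.1 to 14.3.1.4. The only challenge-emergent summary is Table 14.3.1.5, whose footnote says "Note: Only the subset of AEs that are judged to be related to challenge agent have been considered".

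Among the events that meet the AE definition, Protocol 10.3.1 lists exacerbation of an existing illness and "Increase in frequency or severity of a pre-existing episodic condition".

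**The concern.** Participants are inoculated on Day 0 and take their first IMP days later, while AEs are collected from study-specific consent (Protocol 8.5.1). There is therefore a period in which an AE can start on study but before the drug. Suppose such an AE is mild at the first dose and becomes severe or serious on IMP. Under the onset rule it keeps its pre-dose status.

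The between-arm AE tables are where a reader looks for harm from RV299. If the drug aggravated a condition that was already present, those tables could miss it. The severity rows, the SAE row and the row for AEs leading to IMP discontinuation matter most, because they should show the worst that happened on treatment.

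**Working it through.** The plan gives no figure to reproduce. The check is to find the window and then follow one event through the definitions and tables.

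**Step 1: the window.** The SAP compares dates, not times. An AE that starts on the day of the first dose, even before the dose, counts as treatment-emergent. So does an AE whose onset date is missing or partial and cannot be placed, unless its stop date shows otherwise. If the first dose is on Day *d*, the exposed dates run from Day 0 (after inoculation) to Day *d* - 1, which is *d* calendar dates. SAP 6.1 puts the first dose between the evening of Day 2 and the evening of Day 5.

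| First IMP | Exposed onset dates | Number of dates |
|---|---|---|
| Day 2 | Days 0-1 | 2 |
| Day 3 | Days 0-2 | 3 |
| Day 4 | Days 0-3 | 4 |
| Day 5 | Days 0-4 | 5 |

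**Step 2: the class.** Take an AE with onset on Day 1, first IMP on Day 3, and a rise from mild to severe on Day 4, kept as one record. Its onset is not before inoculation, so it is not pre-treatment. Its onset is before the first-dose date, so it is not treatment-emergent. It is challenge-emergent only.

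**Step 3: the outputs.**

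| Output | Is this AE shown? |
|---|---|
| 14.3.1.1 Overall TEAE summary (severity, SAE, related, withdrawal and IMP-discontinuation rows) | No |
| 14.3.1.2 SOC/PT | No |
| 14.3.1.3 SOC/PT/severity | No |
| 14.3.1.4 Related to RV299 | No |
| 14.3.1.5 Related to challenge agent | Depends on recorded relationship; no severity rows |
| 14.1.1 Disposition | Yes, if the AE led to stopping IMP |
| Listing 16.2.7 | Yes, with dates, flags and severity |

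The AE is in 0 of the 4 IMP adverse event tables. If it led to stopping IMP, the disposition table would count it and the discontinuation row of Table 14.3.1.1 would not, so the two could disagree.

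**Step 4: entry to Table 14.3.1.5.** The end of SAP 10.9.1 treats *Unlikely* and a missing relationship as related for this purpose, and the shell has rows for both. The shell's footnote omits *Unlikely*. On the SAP text only AEs recorded as not related to the virus drop out; on the footnote those recorded as *Unlikely* drop out too.

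**Step 5: does another rule bring the event back?** The SAP's greatest-severity rule applies when a participant has several events with the same preferred term. It does not move the onset of one continuing record. Protocol 10.3.6.1 lists onset, grade and resolution among the items to record and has no rule for a grade that changes. Protocol 10.3.1 is at most ambiguous: it counts worsening of an existing condition as an AE and excludes a condition present before study intervention only if it does not worsen. However, Protocol Table 6-1 lists the challenge virus as a study intervention as well, so it is unclear whether an AE that starts after challenge is pre-existing in that sense.

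**Step 6: size.** With 40 planned per arm, one participant missed lowers an arm's incidence by 1/40 = 2.5 percentage points. This is the weight of one participant, not a forecast. The documents give no rate for AEs that start in the window, continue and worsen.

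**The case against.** The strongest reply is that the definition matches the stated safety endpoint, which counts AEs from the first administration of IMP; that the rule is the same in both blinded arms; and that few events can be affected. Protocol 10.3.1 and 10.3.6.2 keep typical diary symptoms, expected pyrexia and expected respiratory signs out of the AE record unless they meet the AE definition and are clinically significant. An illness that is trivial before dosing and significant afterwards may well first become an AE after dosing, and so be treatment-emergent already. Worsening of diary symptoms is also tabulated by arm relative to IMP in Table 14.2.3.3. Site instructions, which are not in these documents, may call for a new record on worsening, and a new onset would satisfy the existing rule.

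The points on frequency and site practice stand, and they keep this a minor matter. The endpoint wording does not say how to treat worsening after the first dose. Equal rules in both arms do not help if the drug causes the worsening, because the missed events would then fall mainly in the RV299 arm. Protocol 9.4.7 also describes AE summaries by SOC, PT and arm without a treatment-emergent limit, and SAP 11 does not list that narrowing as a change.

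A reader might infer that all IMP safety tables are blind to such worsening. The documents do not support that: SAP 10.9.2, 10.9.3 and 10.9.6 use a pre-IMP baseline for laboratory values, vital signs and ECG, so numeric worsening would still show there. Nor do they support reading the whole interval up to the first dose as exposed, because the date rule already captures the day of dosing.

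**Conclusion.** The point holds as a gap in the four IMP adverse event tables. An AE with onset after inoculation and before the first-dose date (2 to 5 calendar dates, depending on the start of dosing) that rises in grade or becomes serious on IMP is not counted in Tables 14.3.1.1 to 14.3.1.4 if it stays on one record. If it reaches Table 14.3.1.5, its grade is not shown there; if it does not, Listing 16.2.7 is the only AE output that contains it.

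This rests on one assumption that the documents leave open: that the site does not open a new AE record when an ongoing event worsens. The number of events is unknown and probably small. It would be too strong to infer that AEs ongoing at the first dose will be common, or that a between-arm safety comparison will be materially distorted; the documents give no data for either. The case for change is that the remedy is cheap and the rows affected are the ones that matter most if an event does occur.

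**What to change.** 1. In SAP 10.9.1, count an AE as treatment-emergent if it starts on or after the first-dose date, or if it starts earlier and increases in grade or becomes serious on or after first IMP. Change the footnotes of Tables 14.3.1.1 to 14.3.1.4 to match.
2. Add an eCRF completion instruction that a post-dose increase in grade of an ongoing AE is recorded with its own date, so that the worst post-dose grade enters those tables. If this is done as a new line with its own onset, the current onset rule already captures it; the wider definition then covers events that become serious without a change in grade.
3. If the eCRF cannot change, add a challenge-emergent table by SOC, PT, severity and arm that is not restricted by relationship. It uses data already collected. It would show the recorded grade, though not whether that grade was reached before or after the first dose.
4. Reconcile the treatment of *Unlikely* between the text of SAP 10.9.1 and the footnotes of Tables 14.3.1.4 and 14.3.1.5.

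The cost is one SAP sentence, the footnote edits and one site instruction, or else one extra table. The downside is slightly higher AE counts in both arms.

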10.3.6.3. Assessment of Intensity

The term 'severe' is often used to describe the intensity (severity) of a specific event. This is not the same as 'serious' which is based on participant/event outcome or action criteria.

The PI/investigator will use the CTCAE grading scale as a reference when collecting, reporting, and clarifying database queries of AEs, SAEs, and adverse reactions.

The severity of an AE that does not appear in the CTCAE grading scale should be determined according to the definitions in [Table 10-2](#).

Table 10-2: Classification of Adverse Events Severity

Grade	Classification	Definition
Grade 1	Mild	Mild level of discomfort, and does not interfere with regular activities
Grade 2	Moderate	Moderate level of discomfort and significantly interferes with regular activities
Grade 3	Severe	Significant level of discomfort and prevents regular activities
Grade 4	Life threatening	Extreme limitation in activity, significant assistance required; significant medical intervention/therapy required, hospitalisation or hospice care probable

An event is defined as 'serious' when it meets at least one of the predefined outcomes as described in the definition of an SAE, NOT when it is rated as severe.

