Treatment Group	Participant	Days from IMP administration to planned discharge	Sum Total Symptom Score (from IMP administration to planned discharge)	Peak Total Symptom Score (from IMP administration to planned discharge)	Peak Daily Total Symptom Score (from IMP administration to planned discharge)	Time to Symptom Resolution from IMP administration (days)	Time to Symptom Resolution from Peak Symptom after IMP administration (days)	Time to Peak Total Symptom Score from IMP administration (days)
xxxxxx	xxxxxx	XX	XX	XX	XX	XX	XX	XX

Note: Derivations made for 10-items of the 13-item diary card.

Programming Note: Place the endpoints that are not by study day onto the first row for each participant.

Listing 16.2.6.4.1
Mucus Weight and Tissue Bag Distribution

Treatment Group	Participant	Study Day	Date Collected	Tissue Bag Distribution		Tissues Taken	Total Tissues Taken	Mucus Weight (g)	Total Mucus Weight (g)	Comments
				Time Collected/Dispensed	hh:mm					
xxxxxx	xxxxxx	xx	ddmm/yyyy			xxxx	xxxx	xxxx	xxxx	

Programming note: The Total Mucus Weight and Total Tissues Taken will be listed against the Day 12 observation.

Listing 16.2.6.5.1
Nasopharyngeal Swab: Respiratory Virus Screen/Rapid Viral Antigen Test

Treatment Group	Participant	Sample Collection Date / Time (Study Day)	Result	Comments
xxxxxx	xxxxxx	ddmmyyyy / hh:mm (xx)	Positive / Negative	xxxxxxxx

Listing 16.2.6.6
Plasma PK Parameters

Treatment Group	Participant	Day	PK Parameter	Units	RV299	Comments
xxxxxx	xxxxxx	XXX	XXX	XXX	XXX	xxxxxxxx

Listing 16.2.7
Adverse Events

Treatment Group / Participant /AE Number	MedDRA SOC / Preferred Term [1] / Adverse event (verbatim)	Start Date Time (study day) / Stop Date Time (Study day)	TE [2] / CE [3] / Severity / Frequency [4]	SAE / Serious Criteria [5]	Outcome [6] / Action Taken IMP [7] / Action Taken [8] /	Related to [9] IMP / Challenge Agent / Concomitant medication / Procedure / Other	Comments
xxxxxx / xxxx / xx	xxxxxxxxx/xxxxxx/xxxxxx	ddmmmyyyy hh:mm (xx) / ddmmmyyyy hh:mm (xx)	Yes or No / (xx) / Yes or No / Mild, Moderate, Severe, Life- Threatening / xx	Yes or Blank / xx	x / x / x	x / x / x / x / x	xxxxxxxxxxxx xxxxxxxxxxxx

TE = Treatment Emergent. SAE = Serious Adverse Event.

[1] MedDRA Version 24.0.

[2] An AE occurring on or after the first administration of IMP.

[3] An AE occurring on or after the challenge agent inoculation.

[4] Freq = Frequency. For frequency categories, C = Continuous, I = Intermittent, S = Single Episode.

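### The SAP's two by-arm severity tables for adverse events stop at severe, although the protocol and the SAP's own listing have a fourth level, life-threatening

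*SAP*

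**What the plan says.** **Scale used for grading.** Protocol 10.3.6.3 takes CTCAE as the reference and applies Table 10-2 to events that CTCAE does not cover. Table 10-2 has four grades. The fourth, life-threatening, is separate from Grade 3 severe and is defined as "Extreme limitation in activity, significant assistance required; significant medical intervention/therapy required, hospitalisation or hospice care probable".

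**Scale used for listing.** SAP Listing 16.2.7 allows the severity values "Mild, Moderate, Severe, Life- Threatening".

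**Scale used for tabulating.** SAP 10.9.1 asks for the "number of participants with events (also split by severity; mild, moderate, severe), number of participants with SAEs". Two shells in SAP 14 split by severity:
- "Overall Summary of Treatment Emergent Adverse Events", listed in SAP 13.2 as Table 14.3.1.1
- "Treatment Emergent Adverse Events by System Organ Class, Preferred Term and Severity", Table 14.3.1.3

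Both have rows for mild, moderate and severe only.

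**Worst-case rules.** For repeats of one preferred term, SAP 10.9.1 says: "It will be assigned the greatest observed severity and the strongest relationship to IMP among those events". The footnote to the overall summary says that if a participant has more than one event, "then the event with the worst severity or strongest relationship is included in the relevant level of summarisation". The footnote to Table 14.3.1.3 is narrower: "If a participant experienced a specific event more than once then the event with the worst severity is summarised".

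**The concern.** The data will be recorded on four levels and tabulated on three, with no instruction for the fourth. Because the overall summary places each participant at the worst grade, a participant whose worst event is Grade 4 cannot fall back into a lower row. The severity rows then fail to add up to the participants with any event, and the category left out is the most severe one.

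The severity split exists to let a reader compare the arms on the intensity of events. The protocol treats life-threatening as a level of its own: it is separate from severe in Table 10-2, and section 7.5 names it alongside severe when describing when enrolment may be halted. A by-arm severity table should be able to show it.

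**Working it through.** The plan states no figure on this point, so the check sets the passages side by side and then counts where one participant would fall.

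**Step 1. Severity levels in each place**

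| Place | Levels | Life-threatening included? |
|---|---|---|
| Protocol Table 10-2 | 4 | Yes |
| SAP Listing 16.2.7 | 4 | Yes |
| SAP 10.9.1 text | 3 | No |
| Shell, overall TEAE summary (14.3.1.1) | 3 | No |
| Shell, Table 14.3.1.3 | 3 | No |

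The SAP therefore differs from the protocol and also from itself.

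**Step 2. Is there a rule that reconciles them?** None was found. SAP 10.9.1 does not merge Grade 4 into severe. The six changes from the protocol in SAP 11 do not mention severity. The two severity shells carry no programming note about extra categories, whereas the demography shell (Table 14.1.2) does tell the programmer to add a category when one is needed. Of the five AE tables in SAP 13.2, only these two split by severity, so no other table fills the gap.

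**Step 3. Overall summary.** In one arm, let A be the number of participants with any TEAE and k the number whose worst TEAE is Grade 4. Each participant is placed once, at the worst grade, so

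Mild + Moderate + Severe = A − k.

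Percentages use the safety population. With the planned 40 per arm the shortfall is k/40:
- k = 0: no shortfall
- k = 1: 1/40 = 2.5 percentage points
- k = 2: 2/40 = 5.0 percentage points

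Here the footnote works across all of a participant's events. A participant with one Grade 4 event and one mild event is therefore in none of the three severity rows.

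**Step 4. Table 14.3.1.3.** The SOC and PT lines of this shell hold no counts of their own; the counts sit only in the mild, moderate and severe rows beneath them. A Grade 4 event therefore has no cell in this table. The worst-severity footnote covers only repeats of the same event, so the participant's milder events under other preferred terms keep their PT-level rows.

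**Step 5. Where the participant still appears by arm**
- the any-AE row of the overall summary
- the table of TEAEs by SOC and PT
- the SAE row, if a seriousness criterion is met
- the related, withdrawal or IMP-discontinuation rows, if they apply

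None of these shows the grade. Among the planned AE outputs, the grade appears only in Listing 16.2.7.

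**The case against.** The strongest reply is that little is lost. The event is counted by arm in several places (Step 5). Many Table 10-2 Grade 4 events would probably be serious as well, since the definition itself expects probable hospitalisation and protocol 10.3.4 counts life-threatening and important medical events as serious. For an abnormal blood count at a scheduled visit, the haematology table gives minimum, maximum and change from baseline by arm. Such events may also be rare: protocol 2.2.1 reports only mild AEs and no SAEs in the earlier study of 32 participants on RV299 and 10 on placebo.

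Much of this stands, and it limits the point. It does not remove the mismatch. Protocol 10.3.6.3 keeps severity and seriousness apart, the SAE row carries no grade, and a table meant to show severity should have a row for every level that can be recorded.

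Four stronger readings are tempting, and the documents do not support them:
- *The worst events would be visible only in a listing.* They remain in the any-AE row and the SOC/PT table. Only the grade drops out of the tables.
- *The worst-severity rule also strips the participant's milder events from both tables.* That is so for the participant-level rows of the overall summary. In Table 14.3.1.3 the rule reaches only repeats of the same event.
- *A Grade 4 event is likely enough in this trial to put a probability on the gap.* The documents give no Grade 4 risk, so any probability would only restate an assumed input.
- *A Grade 5 row is missing too.* Table 10-2 and Listing 16.2.7 both stop at life-threatening, and death is recorded as an outcome. A Grade 5 row would rest on CTCAE content that the documents do not reproduce.

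**Conclusion.** The inconsistency is real and follows from the text alone. Programmed as written, the overall summary would understate its severity rows by one participant for each participant whose worst TEAE is Grade 4 (2.5 percentage points each, assuming 40 per arm in the safety population), and Table 14.3.1.3 would have no cell for the Grade 4 event. If no Grade 4 TEAE occurs, there is no effect.

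This is a correction to table reporting. A reader might infer from the word life-threatening that participant protection or stopping decisions are affected. They are not: protocol 7.5 places those decisions with the investigator and the sponsor's medical expert on review of the data, and the final tables play no part in them. No efficacy endpoint, estimate or test is involved.

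**What to change.** In SAP 10.9.1, extend the severity split to mild, moderate, severe and life-threatening. Add a life-threatening row to the shell for Table 14.3.1.1, and one under each SOC and PT in the shell for Table 14.3.1.3. The severity rows of the overall summary will then add up to the participants with any AE, provided every event has a recorded grade, and that sum can serve as a programming check.

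The cost is one phrase in the text and one extra level in each of two shells. No new data are needed, because the grade is already collected and listed. The change should be made before unblinding.
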